- 3) To assess the effect of treprostinil inhalation on oxygenation in patients with acute hypoxic respiratory failure with, or at risk for, development of ARDS
- 4) To assess the effect of treprostinil inhalation on various biomarkers thought to be related to the pathogenesis and/or clinical course of ARDS.

We propose a proof of concept, double blinded, placebo controlled study of inhaled treprostinil for patients with "at-risk" or early ARDS. Early, or pre-ARDS will be defined as acute hypoxemia and unilateral pulmonary infiltrates in patients presenting with conditions that are conducive to ARDS (e.g. pneumonia, sepsis, aspiration, trauma) but do not yet meet criteria for ARDS: require mechanical ventilation, bilateral infiltrates on CXR, and PaO_2/FiO_2 ratio < 300. The primary outcome will be PaO_2/FiO_2 ratio. We will also measure other physiologic and clinical outcomes and levels of inflammatory and pro-fibrotic biomarkers. This exploratory initial study will enroll 30 patients to assess feasibility and safety in this population.

Hypothesis:

- 1. Treprostinil inhalation is safe at planned dose titration in patients with acute hypoxemic respiratory failure
- 2. Treprostinil will improve oxygenation and other secondary outcomes related to mechanical ventilation initiation and duration, as well as exhibit effects on ARDS-related pro-inflammatory and pro-fibrotic biomarkers.

Study Design:

- 1) Single Center, proof of concept, 2:1 active drug to placebo controlled, double-blinded
- 2) Target of 30 patients enrolled
- 3) Patients will be randomized to receive either treprostinil or saline inhalation placebo
- 4) Patients will be followed to hospital discharge or day 28, whichever comes first. Those discharged prior to day 28 will be assumed free of mechanical ventilation and alive unless readmitted in that period. This will be confirmed by phone.

Sample Size/Interim Monitoring:

1) This is primarily a feasibility, safety and proof of concept trial.

Version: 02-09-2018

- 2) The primary endpoint is Change in PaO₂/FiO₂ ratio from Study Day 0 to 2, 7
- 3) Trial progress will be monitored by an independent Data and Safety Monitoring Board to determine if the study should stop for safety reasons. The first interim review will occur6 months following enrollment of the first patient or after the first 15 patients (which-ever occurs first) have been enrolled.

Inclusion Criteria:

- 1) Adults age 18-80 years.

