- 2) Acute onset need for 4 LPM or more of supplemental oxygen to maintain $PaO_2 > 60$ mmHg or arterial O_2 saturation > 90% by pulse oximetry.
- Acute unilateral pulmonary infiltrate/s on chest radiograph with no clinical evidence of left-sided heart failure. Bilateral infiltrates are acceptable as long as all other inclusion/exclusion criteria are met.

"Acute onset" is defined as follows: the duration of the hypoxemia criterion (#2) must be less than 96 hours and the chest radiograph criterion (#3) must be ≤ 28 days at the time of randomization. We acknowledge there is some difficulty determining absolute acuity with a 28 day window for the chest radiograph criterion, but this criterion is consistent with multiple NHLBI ARDSnet studies to date.

Patients must still meet inclusion criteria at the time of informed consent and randomization. Randomization is defined as the time that the IDS is contacted and informed about stratification of non-trauma and trauma patients. Patients that no longer meet eligibility criteria at the time of randomization are eligible to be re-screened if they meet inclusion criteria eligibility again.

Exclusion Criteria:

- 1) No consent/inability to obtain consent
- 2) Presence of pulmonary embolism
- 3) Known diffuse alveolar hemorrhage from vasculitis
- 4) Known pre-existing severe obstructive or restrictive lung disease (FEV 1 < 40% predicted, TLC < 50 % predicted) or need for long-term supplemental oxygen therapy
- 5) Known significant left ventricular systolic dysfunction with LVEF < 40% on echocardiogram.
- 6) Mean arterial pressure < 65 mmHg
- 7) Need for norepinephrine or dopamine dose > 12 mcg to maintain MAP > 65 mmHg
- 8) Severe chronic liver disease (Child-Pugh Score 11-15)

Measure	1 point	2 points	3 points	Units
Bilirubin (total)	<34 (<2)	34-50 (2-3)	>50 (>3)	μmol/l (mg/dl)
Serum Albumin	>35	28-35	<28	g/l
INR	<1.7	1.71-2.20	> 2.20	no unit
Ascites	None	Suppressed with medication	Refractory	no unit
Hepatic Encephalopathy	None	Grade I-II (or suppressed with medication)	Grade III-IV (or refractory)	no unit

- 9) Moribund patient not expected to survive 24 hours
- 10) QTc interval > 550 ms on screening bedside strip or electrocardiogram
- 11) Pregnancy or breast feeding (Women of childbearing potential, defined as < 60 years of age, will require pregnancy testing.)
- 12) Burns > 40% total body surface
- 13) Acute Neurological Disease (that may impair the ability to ventilate without assistance

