Analysis of covariance (ANCOVA) will be used to compare trends for the primary outcome PaO₂/FiO₂ ratio between days 0 and 7 between intervention and control patients. PaO₂/FiO₂ ratio is measured at baseline (day 0), and days 2, 7,. The difference in treatment groups for change from baseline to day 7 and days 2 will be estimated using an ANCOVA adjusting for baseline value. 95% and 80% confidence intervals for the difference in least squares means will be calculated. Due to small sample sizes, substantial normality departures due to skewness will be assessed. As a supportive exploratory analysis, if a number of patients do not have a day 7 assessment, a mixed linear model for repeated measures (MMRM) of PaO₂/FiO₂ ratio at days 0, 2, and 7 will be explored. The focus of the analysis is to assess preliminary evidence of efficacy. Sample size permitting, trends will be evaluated separately in trauma and non-trauma patients.

The secondary efficacy outcome, 28 day ventilator free days, is defined as days alive and free of mechanical ventilation during the first 28 days after randomization. Patients who die will receive 0 ventilator free days. Patients who are discharged free of mechanical ventilation prior to day 28 will be assumed to remain free of mechanical ventilation unless they are readmitted. Ventilator free days is expected to be skewed. Comparisons between treatment groups will focus on 95% and 80% confidence intervals of the Hodges-Lehman estimator for location shift.

Time until mechanical ventilation and time until death will be described via Kaplan-Meier survival curves.

Remaining efficacy outcomes and biomarkers will be analyzed with similar methods. Categorical outcomes will be characterized by odds ratios and assessed with chi-squared tests or Fisher's exact tests. Biomarker values change from baseline will be assessed comparing treatment groups overall and stratified by whether the acute lung injury was resolved by day 28.

Sample size calculation

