Sample size calculations are based on simple t tests. Assuming a change in PaO_2/FiO_2 ratio of 15 in the intervention group and 10 in controls, a standard deviation of 6 (effect size of 0.833), and power of 0.80, the study would require 34 patients in the intervention group and 17 patients in the control group for a 2-sided test with significance level p < 0.05. While we will not approach these numbers, they serve to provide a framework as to the sample size needed to observe clinically meaningful changes in oxygenation as statistically significant. This current proposal centers on safety and feasibility, and thus does not meet the statistical criteria needed to observe minimally significant changes in oxygenation. The planned sample size of 30 total participants has 80% power to produce a 2-sided 80% confidence interval with lower confidence limit above 0 if the true effect size is 0.833.

Twenty-eight day ventilator-free days is a continuous variable. The mean 28 day ventilator free

Version: 02-09-2018

days for the control group of the most recent ARDS network trial was 15 days (95% CI 14.1 – 15.9). The patients enrolled for this trial will have significantly more ventilator free days as a number of them will not require mechanical ventilation at all. A study with 100 patients would have a power of 0.8 to show a 3 day difference in 28 day ventilator free days assuming a value of 22 for controls and 25 for intervention patients, with a SD of 5 days. Since this is an initial, smaller feasibility and proof of concept trial, we will not be able to obtain this level of statistical rigor.

Study feasibility will be assessed by enrollment rate over the first 6 months of the study. If the enrollment rate at that time suggests high feasibility such that the enrollment target of 30 patients can be exceeded easily within the funded enrollment period, we will consider amending the protocol to enroll a small number of additional subjects. This will be discussed and reviewed by the study DSMB. [name], Department of Biostatistics, UNC will provide statistical support.

Part 3. Data Collection and Site Monitoring

Data Collection

Research coordinators will collect data and enter it directly into a computer-based data entry system managed by the TRACS institute or on paper data forms.

Site Monitoring

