Patients with ARDS have a high risk of 28-day mortality, which is approximately 45% in general ICU populations. This is because ARDS tends to be part of a syndrome of multi-organ failure that accompanies underlying severe conditions such as septic shock, severe pancreatitis, and multilobar pneumonia in patients with multiple underlying comorbidities. For that reason, 28-day mortality is the most common clinical outcome for large trials of ARDS, and in those large trials, stopping rules for safety or futility are built around 28-day mortality.

This study is a small pilot study of feasibility and safety enrolling patients with early ARDS not yet requiring mechanical ventilation. Due to its small size, a *statistical* stopping rule based on mortality or even Grade IV Adverse events is not possible. This has been confirmed by additional review by the study's statistician. Therefore a *clinical* stopping rule based on Grade 4 events or complete respiratory failure requiring intubation and mechanical ventilation, (an event that is intermediate to possible mortality in ARDS) has served as the stopping rule for this study to date.

The principle conditions for suspension of study enrollment and review of safety by the DSMB will be:

After enrollment of the first 30 patients:

- An imbalance of greater than 4 to 1 (given 2:1 randomization scheme) of any Grade 4 Adverse event from the NIH Common Terminology Criteria for Adverse Events (CTCAE)
- An imbalance of greater than 4 to 1 (given 2:1 randomization scheme) in the number of patients requiring intubation and mechanical ventilation in favor of intervention.
- A 28-day mortality rate of greater than 60% in either study arm, reflecting a rate measurably higher than expected in ARDS.

Of note: To reduce potential bias, the relationship of any Grade 4 or 5 events to study drug will be adjudicated by an expert in pulmonary hypertension and critical care, [name], who is not participating in the study and will be blinded for the assessments.

Version: 02-09-2018

Version: 02-09-2018

References:

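### The 60% mortality suspension limit is benchmarked on general-ICU ARDS rather than on the early, unventilated patients enrolled, and has almost no ability to flag harm in them

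*Combined protocol and SAP*

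**What the plan says.** The Study Stopping Rules section opens with its reference rate: "Patients with ARDS have a high risk of 28-day mortality, which is approximately 45% in general ICU populations". It then describes the trial differently: "This study is a small pilot study of feasibility and safety enrolling patients with early ARDS not yet requiring mechanical ventilation". One of its three conditions for suspending enrolment is nevertheless "A 28-day mortality rate of greater than 60% in either study arm, reflecting a rate measurably higher than expected in ARDS". The other two are imbalances of more than 4 to 1 in Grade 4 adverse events and in intubations. All three are stated to apply once 30 patients have been enrolled, which is the whole target sample. The section says that a statistical rule is not possible at this size and calls its rule clinical.

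The Exclusion Criteria remove some of the sickest candidates, for example "Moribund patient not expected to survive 24 hours" and patients about to need intubation or non-invasive ventilation.

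For ventilator-free days, the Sample size calculation section does adjust for the milder population. It cites a mean of 15 days for ARDS network controls and then says "The patients enrolled for this trial will have significantly more ventilator free days as a number of them will not require mechanical ventilation at all". It plans on 22 days for controls and 25 for the intervention, with an SD of 5. The Efficacy section fixes the scoring: "Patients who die will receive 0 ventilator free days".

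**The concern.** The limit is a number justified by a reference rate, and that rate belongs to a different population. The plan makes the correction for ventilator-free days but not for mortality, and it gives no expected mortality for the patients it will enrol.

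Safety is the trial's first hypothesis, and this is its only numerical criterion on deaths. If the mortality expected in these patients is far below 45%, a limit of 60% could stay uncrossed while the drug did substantial harm. It also tells the DSMB that any rate up to 60% is within what was anticipated.

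**Working it through.** **Inputs.** 30 patients at 2:1, so 20 active and 10 placebo (Study Design; Randomization). Limit above 60% in either arm (Study Stopping Rules). Control mean of 22 ventilator-free days, SD 5 (Sample size calculation). Deaths score 0 and the maximum is 28 (Efficacy).

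**Step 1: reproduce the plan's figure.** The limit has no stated operating characteristics to reproduce, so I checked the calculation that supplies the mean of 22. A difference of 3 with SD 5 is an effect size of 0.6. For 100 patients at 2:1 (33 and 67), two-sided alpha 0.05 assumed, a two-sample t-test has power 0.798. This matches the stated 0.80. At 1:1 the power would be 0.844.

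**Step 2: mortality ceiling from the mean.** If a proportion p dies and scores 0, and every survivor scores the maximum, the mean is 28(1 − p). Setting 28(1 − p) ≥ 22 gives p ≤ 6/28 = 21.4%. At that extreme the SD would be 28 × √(0.214 × 0.786) = 11.5, not 5.

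**Step 3: ceiling from the mean and SD together.** With a proportion p at 0 and a mean of 22, the variance is smallest when all survivors share one value. It is then 22² × p/(1 − p). Requiring this to be at most 5² = 25 gives p ≤ 25/(25 + 484) = 4.9%.

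**Step 4: what the limit requires.** More than 60% of 20 is at least 13 deaths; more than 60% of 10 is at least 7.

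**Step 5: chance of reaching a count in the active arm.** Exact binomial upper tail, P(X ≥ k) with n = 20. The last column is an illustrative lower count, used under fix.

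| True 28-day mortality | P(at least 13 of 20) | P(at least 8 of 20) |
|---|---|---|
| 10% | below 0.001% | 0.04% |
| 15% | below 0.001% | 0.6% |
| 20% | 0.002% | 3.2% |
| 21.4% (6/28) | 0.003% | 4.7% |
| 30% | 0.13% | 23% |
| 42.9% (12/28) | 3.9% | 68% |
| 45% | 5.8% | 75% |
| 60% | 42% | 98% |

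True active-arm mortality must be about 62% for an even chance of crossing the present limit, and about 71% for an 80% chance.

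**Step 6: sensitivity.** With controls at 21.4% and the active arm at 42.9%, the chance that either arm crosses is 4.0%. For active arms of 17 to 23 patients, the active-arm figure at 42.9% ranges from 3.9% to 9.3%. At lower control rates a doubling is less visible still: 15% to 30% gives 0.13% in the active arm, 10% to 20% gives 0.002%, and 4.9% to 9.8% gives less than 0.0001%.

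**The case against.** The strongest reply is that this single line is not the trial's safety monitoring. The DSMB reviews unblinded deaths, intubations and non-invasive ventilation every six months, or once 15 patients have finished if that is sooner. It can ask for further data, Grade 4 and 5 events are adjudicated blind, and two other suspension triggers exist. That stands. A reader might infer that a drug which doubles mortality would pass through the trial unnoticed; the documents do not support this. What they support is that this numerical limit would not be what flags it.

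A reader might also take 21% as the mortality that the plan expects. It is not. It is an arithmetical maximum drawn from an illustrative 100-patient calculation, and the same inputs give about 5% once the SD is used. Nor can actual mortality be fixed from the eligibility criteria, which also admit bilateral infiltrates, ages up to 80, vasopressor support below a set level and high-flow oxygen up to 50 LPM. The result does depend on the control rate: at 35% doubled to 70%, the active arm would cross 77% of the time. But 35% cannot be squared with a control mean of 22 days.

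The plea that the rule is clinical and the sample small explains imprecision. It does not justify a reference rate from another population.

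**Conclusion.** The concern holds as a mismatch of benchmark and population. The 45% reference is more than twice the highest control mortality that the plan's own control mean allows (45/21.4 = 2.1), and the 60% limit is nearly three times it (60/21.4 = 2.8). At the ceiling doubled, the active arm stays below the limit about 96% of the time; at mortality equal to that quoted for general-ICU ARDS, about 94%.

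This rests on binomial deaths, a 20/10 split, known 28-day status for all patients, and the planned control mean of 22 days applying to those enrolled, which is how the text uses it. The doubling is a test scenario of this review and is not in the documents.

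The consequence is limited by the DSMB's periodic review and the other two triggers. It is also bound up with timing: a limit that applies only after all 30 are enrolled can suspend little unless the trial is extended, so changing the threshold alone would alter little in practice.

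**What to change.** In Study Stopping Rules:

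- Replace the general-ICU reference with an explicit expected 28-day mortality for the enrolled population, consistent with the ventilator-free-day assumptions.
- Have the sponsor and DSMB reset the limit from that rate, written as death counts that also apply at the existing DSMB reviews and not only after 30 patients.
- State the operating characteristics beside the rule over a range of control rates.
- Delete or restate the closing justification that the limit is measurably above what is expected in ARDS.

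The last column of the table is an illustration only. A count of 8 of 20 would trigger 4.7% of the time at a true 21.4% (4.6% if the rate is rounded to 0.214), 0.6% at 15% and 0.04% at 10%. It would detect a doubling 68% of the time from 21.4%, but only 23% from 15%, 3% from 10% and 0.04% from 4.9%. It should not be read as the recommended limit: if expected mortality is well below 21%, a lower count would be needed.

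The cost is a wording change in the protocol and the DSMB charter, with no added patients, visits or data. The downside is a small chance of an unnecessary pause for DSMB review, which depends on the count chosen and should be reported with it.

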APPENDIX 1: Guidelines for evidence of infection

1. Infections of the thorax:

- a. Chest x-ray or CT scan showing a new or progressive infiltrate, consolidation, cavitation, collection, or pleural effusion, and a clinical presentation consistent with pneumonia or empyema
- b. Pneumonia can be defined as the presence of new infiltrate (s), absence of a noninfectious explanation and either signs of SIRS as per protocol or purulent sputum production with an identifiable pathogen.
- c. Aspiration Pneumonitis in the acute phase is not considered an infection. However, if SIRS persists > 24 hours after aspiration, then an infectious etiology can be presumed.

2. Abdominal infection:

- a. Perforated viscus or ischemic bowel with either localized peritonitis
- b. Peritoneal fluid with > 250 PMNs
- c. Clinical signs of cholangitis or appendicitis
- d. Clostridium difficile toxin positive with evidence of colon dilation
- e. Suspicion of peritonitis by clinical examination only
- 3. **Skin or soft tissue infection:** Acute onset infection of the skin, such as erysipelas, or infection involving deeper soft tissue
- 4. **Bacterial meningitis:** cerebrospinal fluid analyses if available and a clinical presentation consistent with bacterial meningitis

5. **Urinary Tract:**

- a. Positive test for granulocyte esterase or nitrate in urine, or a positive culture (defined as >10⁵ CFU/mL)
- b. Urinalysis with increased WBC count or positive Gram stain

6. Central Line infections:

- a. Isolation of a pathogen in one or more blood cultures drawn peripherally, or from a central venous catheter/port in place <48 hours
- b. Purulence at insertion site

7. Sinusitis

a. Air fluid levels in sinus seen on CT scan

8. The following are not considered evidence of infection:

- a. Fever of unknown origin
- b. Blood cultures that are considered positive only because of the isolation of a likely contaminant organism
- c. Postoperative hypotension within 24 hours of incision and/or fever without a verified infectious focus.
- d. Leukocytosis alone in the presence of steroid usage is insufficient evidence of infection.
- e. Leukocytosis alone in the presence of connective tissue disorder is insufficient evidence of infection.

APPENDIX 2:

Schedule of Events

Description of Event	Day	Day	Day	Day	Day	Day	Day	Day	Day	Day	Day	Day	Day	Day	Day	Day
Description of Event	0	1	2	3	4	5	6	7	8	9	10	11	12	13	14	28
Inclusion / Exclusion Review	х															
Informed Consent	х															
Screening QTc	х															
Randomization	х															
Physical Examination	х															
Background Assessments	х			and Adr alysis U				story, He	eight; Ge	nder, M	easured	Body W	eight (M	l IBW); Ty	pe of Ho	spital
Baseline Assessments**	availa	ble for t	his 24 ho	our perio	d, the va	alue clos	est to th	hour int e time of measur	f randon	nization	will be re	ecorded.	If no va	lues are	availabl	
** Scoring (APACHE II and LIPS Scores)	х															
** Vital Signs and PaO ₂ ,PCO ₂ , pH; SpO ₂	х															
Available Labs ** Serum AST, ALT	х															
Required: ABG; Albumin; Bilirubin; BUN; Creat; Glucose; HCT; HGB; K; Na; Plt; WBC	х															
** Vasopressor or Inotropes Use	х															
Reference Measurements++	on the	specifi	c variabl		til stoppi	ng of stu		orded us , whiche								
Fluid Intake / Output	х	Х	х	х	х	х	х	х	х	х	х	х				
++ Vital Signs	х	х	х	х	х	х	х	х	х	х	х	х				
Concomitant Medication Use	х	х	х	х	x	x	x	x	x	x	x	x				
(Including Nebulized and Inhaled Medications)	^	^	^	^	^	^	^	^	^	^	^	^				
Lung Injury Score (Chest x-ray)	х			х				х								Х
Modified Brussels Score	х	х	х	х	х	х	х	х	х	х	х	х	х	х	х	
Study Drug Administration	х	х	х	х	х	х	х	х	х	х	х	х				
Blood Pressure Assessments (On Study Day 00, blood pressure will be checked prior to Dose 1 and 30 minutes after; prior to Dose 3 and 30 minutes after; prior to Dose 5 and 30 minutes or after a different dose interval, if the study drug had to be maintained due to an adverse effect. Blood pressure measurements for Study Days 01 through 11 will be captured from the nursing flow-sheets.	х	x	х	х	x	x	x	х	х	x	x	x				
Peak / Trough Specimen Collection (Peak Specimen will be obtained 15min [+/-5min] after Dose 1 on Day 3) (Trough Specimen will be obtained just prior to Dose 2 on Day 3)				х												

Biomarkers Specimen Collection	x			х				х						
(** Baseline specimen collection is prior to study drug administration)	^			^				^						
PaO ₂ / FiO ₂ Ratio (If the subject is still hospitalized)	х		Х					х						
SpO ₂ / FiO ₂ Ratio	х	х	х	х	х	х	х	х	х	х	х	х		Х
SCVO ₂ (if central venous catheter is in place)	х	х	х	х		х		х						
CVP (if central venous catheter is in place)	Х	х	х	х										
SBP / MAP (if arterial line is in place otherwise cuff)	Х	х	х	х	х	х	х	х						
Adverse Events Review	х	х	х	х	х	х	х	х	х	х	х	х		
Hospital Mortality														х
Phone Assessment of Disease Outcomes and Adverse Events														х
Day 28 Mortality														Х

Version: 02-09-2018

Appendix 3

Oxygen Titration Protocol

The goal of the Oxygen Titration Protocol is to maintain a resting oxygen saturation of 90-94%. Brief increases in the research subject's O₂ liter flow for ambulation and exertion can be allowed. However, before each study drug administration, the respiratory therapist should make sure that the research subject is on the lowest amount of oxygenation required to achieve an oxygen saturation of 90-94% before recording their baseline O₂ requirement. Reassessment of oxygen saturation before and after each level should occur. Research subjects will start with a conventional humidified nasal cannula. If oxygen titration is needed, we will titrate from their current nasal cannula flow rate in the following stepwise fashion: 4LPM / 5LPM /6LPM. If there is a need for oxygen titration above 6 LPM, we will utilize a High Flow Nasal Cannula with the flow rate of 20 to 50 LPM. We will titrate the High Flow Nasal Cannula FiO2 in the following stepwise fashion: 50%, 60%, 70%, 80%, 90%, and 100%. The required liter flow will be titrated per patient need/demand. If a patient requires more than 50LPM via HFNC, they will have met our classification of *requiring positive pressure threshold*. If clinically indicated, clinicians that are managing the care of these research subjects can initiate non-invasive ventilation or proceed to intubate prior to a patient reaching 100% O₂ or 50LPM flow rate, per our stepwise fashion.

FiO₂ Conversion Table

FIU ₂ Con	version rable
Conventional Humidified Nasal Cannula Flow Rate	FiO ₂
1 LPM	24%
2 LPM	28%
3 LPM	32%
4 LPM	36%
5 LPM	40%
6 LPM	44%
High Flow Nasal Cannula Flow Rate	FiO ₂
20 LPM to 50LPM	50%
20 LPM to 50LPM	60%
20 LPM to 50LPM	70%
20 LPM to 50LPM	80%
20 LPM to 50LPM	90%
20 LPM to 50LPM	100%
	1

Version: 02-09-2018
